1) Identify the rate at which blindly placed caudal blocks are not within the epidural space 2) Identify the rate at which ultrasound can guide a wrong block into the correct location 3) Identify if lack of heart rate change on incision can predict successful placement when medication administration is successfully confirmed with ultrasound 4) Identify if after using ultrasound to visualize placement, if concentrations of inhaled agents may be reduced in children

Section E: Protocol Risks/Subjects

E1. Risk Category

Category 1: Research not involving greater than minimum risk.

E2. Subjects

Gender:

Both

Age:

Child (3-12 yrs), Infant/Toddler (0-36 mos)

Ethnicity:

All Ethnicities

Primary Language:

English, Spanish

Groups to be recruited will include:

Patients

Which if any of the following vulnerable populations will be recruited as subjects?

Children

Vulnerable populations require special protections. How will you obtain informed consent, protect subject confidentiality, and prevent undue coercion?

Consent will only be obtained from parents/legal guardians. Confidentiality will be maintained by the PI as no patient or provider specific identifiers will be recorded aside from consent parental signature. To avoid undue coercion, consenting parents/guardians will be informed that their willingness to participate will not affect their child's treatment course or ability to get a caudal block or have any impact on their care course.

E3. Pregnant woman/fetus

Will pregnant women and/or fetuses (as described in 45 CFR 46 Subpart B) be enrolled in the research?

No

E4. Neonates

Will neonates of uncertain viability or nonviable neonates (as described in 45 CFR 46 Subpart B) be enrolled in the research?

No

E5. Children

Will children be enrolled in the research?

Yes

Section F: Design/Procedure

F1. Design

Select one category that most adequately describes your research:

c) Pilot

Discuss the research design including but not limited to such issues as: probability of group assignment, potential for subject to be randomized to placebo group, use of control subjects, etc.

Single blinded prospective trial in which all patients serve as their own clinical control group.

Inclusion Criteria:

Children ages 0-84 months Infra-umbilical procedure for which a caudal block is already planned American Society of Anesthesiology classifications of 1,2 or 3

Exclusion Criteria:

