Associated procedures for which caudal does not provide complete analgesia Incarcerated hernias Emergency procedures Local Anesthetic allergy Sacral dimple Rash over sacrum precluding block Parents/legal guardians unable to consent for surgical procedure in English language Foster Care/Child protective services as guardians Parental Refusal for caudal block or study participation American Society of Anesthesiology classifications other than 1,2 or 3

F2. Procedure

Patients meeting inclusion criteria and following informed consent will be brought back to the operating room. General anesthesia will be induced in the standard manner either by inhalation induction or intravenous induction at the discretion of the anesthesia attending of record. The airway will be secured using an

age/weight appropriately sized device, at the discretion of the anesthesia attending of record. The caudal block will ensue in the same manner regardless of the study at the discretion of the anesthesia attending of record. The attending anesthesiologist will perform or instruct the placement of a caudal block according to their standard of practice. At the time of administration of local anesthetic into the caudal space, the study collaborator (SC) will ultrasound the caudal space keeping the provider placing the block blinded to the imaging. The provider placing the block will inject 0.5mL of preservative free saline. The provider will then be asked to state if they are correctly in the caudal space or not. If the provider feels they are not in the caudal space, they will re-do the procedure. If the provider fails to identify incorrect location and this is noted by ultrasound, the SC will inform the provider to re-do the procedure. After a successful injection (as confirmed by ultrasound) is performed, the patient will be prepped for the procedure in standard manner. The inhaled anesthetic will be titrated until the minimal alveolar concentration is between 0.8-1 MAC for age prior to incision. The anesthesia provider will note the heart rate immediately before and after the first surgical stimulation. Data will be recorded de-identified on the sheet (see attached). The study PI will compare MAC hours (exposure to inhaled anesthetic agent) in patients having undergone caudal block with ultrasound confirmation to those in the retrospective group gathered for quality improvement to ascertain if reduction of exposure to inhaled agent was possible.

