Section G: Sample Size/Data Analysis

G1. Sample Size

How many subjects (or specimens, or charts) will be used in this study?

Local: 150 Worldwide: 150

Please indicate why you chose the sample size proposed:

A previous study using ultrasound in children for caudal block demonstrated an incidence of 7.1% subcutaneous bulging (failed block) when ultrasound was not used. Using our primary outcome of determination of block failure rate when performing blind (without ultrasound) and assuming a difference of 20% increase in success rate would alter practice and thus be clinically significant using a one sample mean, alpha of 0.05 and a power of 80% would require an enrollment of 99 patients, each serving as their own control. Assuming a study dropout rate of 10% (unknown sacral dimple, etc.) and requirement for additional patients to perform secondary statistical analyses, 150 patients will be enrolled. Analysis performed with JMP statistical software.

G2. Data Analysis

Provide a description of your plan for data analysis. State the types of comparisons you plan (e.g. comparison of means, comparison of proportions, regressions, analysis of variance). Which is the PRIMARY comparison/analysis? How will the analyses proposed relate to the primary purposes of your study?

Data will be presented as means +/-SD, median (range) and number % when appropriate. Continuous variables will be compared with independent sample t-test or Mann-Whitney U testing for normally distributed data. Odds ratios will be noted for the primary outcome with confidence intervals displayed to achieve CI of 95%. Statistics will be aided by JMP software with P values of <0.05 considered significant.

Section H: Potential Risks/Discomforts

Describe and assess any potential risks/discomforts; (physical, psychological, social, legal, or other) and assess the likelihood and seriousness of such risks:

There are no potential risk of discomfort to the patients As with all studies, there is a small risk of loss of confidentiality or data breach.

Section I: Potential Benefits

Describe potential benefit(s) to be gained by the individual subject as a result of participating in the planned work.

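### Section G2 names only independent-group tests for continuous variables, which do not suit heart rate read twice in the same child (minor; secondary objective 3 only)

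*Combined protocol and SAP*

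**What the plan says.** Section G2 (Data Analysis) has a single rule for continuous variables: "Continuous variables will be compared with independent sample t-test or Mann-Whitney U testing for normally distributed data". It does not say which test goes with which variable. No paired t-test, signed-rank test or change score appears anywhere in the document.

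Two continuous measurements are described in Section F2 (Procedure):

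- **Heart rate.** "The anesthesia provider will note the heart rate immediately before and after the first surgical stimulation". Each child gives two readings.
- **MAC hours.** "The study PI will compare MAC hours (exposure to inhaled anesthetic agent) in patients having undergone caudal block with ultrasound confirmation", the comparator being the retrospective quality-improvement group. These are separate groups of children.

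Heart rate serves the third objective in Section D: "Identify if lack of heart rate change on incision can predict successful placement when medication administration is successfully confirmed with ultrasound". Section F1 describes the study as a "Single blinded prospective trial in which all patients serve as their own clinical control group".

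F2 also fixes who reaches the heart-rate reading: "After a successful injection (as confirmed by ultrasound) is performed, the patient will be prepped for the procedure in standard manner".

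**The concern.** Two readings from one child are usually correlated. An independent-groups test ignores that correlation. When it is positive, the test uses a standard error that is too large, its type I error falls below the nominal 5%, and it loses power.

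The direction of the error matters here because objective 3 is about an absence of heart-rate change. A test that too rarely finds a change leans towards the answer that a reader would find reassuring. A non-significant p-value could be reported as no change when the test was simply insensitive.

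There is also a drafting slip. As written, both tests, including the Mann-Whitney U, apply to normally distributed data, and no test is assigned to data that are not normal.

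**Working it through.** **The plan's own figure.** There is none to reproduce. The document gives no power, SD, expected change or correlation for heart rate. The 99 patients in Section G1 were derived for block failure, which is binary and not touched by this rule.

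**Inputs.**

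- From G1: 150 enrolled and 10% dropout, so n = 150 × 0.9 = 135 evaluable children. Alpha is 0.05, taken as two-sided.
- Assumed, not in the document: equal SD before and after, and within-child correlation r from 0 to 0.8.

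**Formulas.** Shifts are in SD units.

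- True standard error of the mean change: sqrt(2(1 − r)/n).
- Standard error used by the unpaired test: sqrt(2/n).
- Ratio of the two: k = 1/sqrt(1 − r).
- Critical t: 1.978 paired (134 df), 1.969 unpaired (268 df).
- Unpaired type I error: 2 × [1 − Φ(1.969k)].
- Noncentrality giving the paired test 80% power: 2.822. Unpaired power at that same shift: Φ(2.822 − 1.969k).

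Worked at r = 0.5: k = 1/sqrt(0.5) = 1.414 and 1.969 × 1.414 = 2.784. Type I error = 2 × [1 − Φ(2.784)] = 0.5%. Power = Φ(2.822 − 2.784) = Φ(0.038) = 51%.

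| r | k | Unpaired type I error | Unpaired power where paired is 80% |
|---|---|---|---|
| 0 | 1.000 | 4.9% | 80% |
| 0.1 | 1.054 | 3.8% | 77% |
| 0.3 | 1.195 | 1.9% | 68% |
| 0.5 | 1.414 | 0.5% | 51% |
| 0.8 | 2.236 | 0.001% | 6% |

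Simulation at r = 0, 0.3, 0.5 and 0.8 agrees: power 80%, 68%, 52% and 6%.

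**Smallest shift detectable with 80% power.** Paired: 2.822 × sqrt(2(1 − r)/135). Unpaired: 1.969 × sqrt(2/135) + 0.842 × sqrt(2(1 − r)/135).

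- r = 0.3: 0.29 SD paired, 0.33 SD unpaired.
- r = 0.5: 0.24 against 0.31 SD.
- r = 0.8: 0.15 against 0.28 SD.

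**Equivalent number of children.** The paired test detects the unpaired test's smallest shift with about 106 children at r = 0.3 and about 82 at r = 0.5. Misusing the unpaired test on 135 children therefore wastes about 135 − 106 = 29 and 135 − 82 = 53 of them.

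**Where it stops mattering.** For a shift of 0.5 SD, simulated power, paired against unpaired, is 98.3% against 98.4% at r = 0, 99.8% against 99.4% at r = 0.3, and 100.0% against 99.8% at r = 0.5. Both are 100.0% at r = 0.8.

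**The case against.** The strongest reply is that the document never plans the analysis that would do the damage. G2 is a general sentence with a proper use, namely MAC hours against the retrospective group. If each child's change were compared between groups, an independent-samples test would also be valid. Objective 3 reads more naturally as a per-child classification than as a mean shift. The only heart-rate criterion in the document, the quality-improvement review's rise of more than 20%, is of that kind. A classification is summarised as a number and percentage, which G2 already provides for, and the t-test rule would not touch it. The error is conservative, is confined to a secondary objective of a self-described pilot, and can be cured at analysis.

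Most of this stands, and it is why the point is minor. It does not remove the point. G2 is the only written rule for continuous data, and an analyst who followed it with the two readings would use the wrong test. F2 describes no between-group heart-rate comparison for which the rule would be right.

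Three stronger readings are tempting and not supported:

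- **That the plan commits to an unpaired before/after test.** It does not. No section matches a test to heart rate.
- **That the own-control design proves a paired heart-rate analysis was intended.** The statement in F1 is general. The one in G1, "would require an enrollment of 99 patients, each serving as their own control", belongs to the block-failure calculation.
- **That the loss would use up the extra patients G1 enrols for secondary analyses.** The margin of 135 − 99 = 36 evaluable children is measured from a number derived for block failure, so it is no benchmark for heart rate. Even taken at face value, the loss at r = 0.3 is about 29, which is less than 36.

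**Conclusion.** The point holds as a minor one, for secondary objective 3 only. The one rule in G2 is wrong for paired heart-rate readings if it is used on them, and its wording on normality needs correcting in any case. The primary outcome is unaffected.

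The direction, too conservative with lost power, holds for any positive within-child correlation. The size cannot be fixed from the document and rests on the assumed r and equal SDs: from no loss at r = 0 to 6% power in place of 80% at r = 0.8, and of no practical importance for a shift of 0.5 SD.

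A reader might infer that a paired test would settle objective 3. It would not. Under F2, children are prepped only after an ultrasound-confirmed injection, so there is no planned group of misplaced blocks to compare with. Neither a mean change nor a proportion among confirmed blocks is a predictive value.

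**What to change.** Replace the G2 sentence with text such as:

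> Continuous variables measured in separate groups, such as MAC hours versus the retrospective group, are compared with the independent-sample t-test if normally distributed or the Mann-Whitney U test if not. Heart rate before and after first stimulation is compared within child, by paired t-test, or by Wilcoxon signed-rank test if non-normal, with the mean or median change and its 95% CI.

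For objective 3, also report the proportion of ultrasound-confirmed blocks without heart-rate change, with a 95% CI, and state that it describes confirmed blocks only. The authors must supply the per-child definition of heart-rate change and fix it in advance. In doing so they should reconcile two passages: the quality-improvement review set its criterion of more than 20% at above 1 MAC, whereas F2 says "The inhaled anesthetic will be titrated until the minimal alveolar concentration is between 0.8-1 MAC for age prior to incision". The document does not say whether the criterion carries over.

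The cost is one sentence reworded, two added and one definition written, with no new data. Precision would be adequate for description. With 135 children, 122/135 (90%) gives a Wilson 95% CI of 84% to 94%, and 108/135 (80%) gives 72% to 86%.

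### G2 puts its only confidence interval for the primary outcome on an odds ratio with no named comparator, although that outcome is a single proportion: the failure rate of blind placement

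*Combined protocol and SAP*

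**What the plan says.** Section D lists as its first objective: "Identify the rate at which blindly placed caudal blocks are not within the epidural space". G1 repeats this as the outcome on which the study is sized: "Using our primary outcome of determination of block failure rate when performing blind (without ultrasound"). Both describe one rate in one cohort.

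The G2 form asks: "Which is the PRIMARY comparison/analysis"? The answer does not say. Its descriptive sentence is "Data will be presented as means +/-SD, median (range) and number % when appropriate", which would cover the rate without an interval. The only inferential statement tied to the primary outcome is "Odds ratios will be noted for the primary outcome with confidence intervals displayed to achieve CI of 95" per cent. A general significance threshold of 0.05 follows, with no test of a proportion attached to it.

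G1 sizes the study by a one-sample mean with alpha 0.05 and 80% power, "assuming a difference of 20% increase in success rate would alter practice", and concludes that this "would require an enrollment of 99 patients, each serving as their own control". Its only input rate is a previous study that "demonstrated an incidence of 7.1% subcutaneous bulging (failed block) when ultrasound was not used". After 10% dropout and an allowance for secondary analyses, 150 are to be enrolled. The background section gives a second rate, 18% from local quality-improvement data, with failure defined by a heart-rate rise at incision.

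**The concern.** Objective 1 asks how often blind placement misses. An interval on an odds ratio does not answer that, and an odds ratio cannot be formed until someone says what the failure odds are compared with. The documents offer several candidates: the same patients after the re-do, the provider's statement against the ultrasound verdict, the published 7.1%, the local 18%, or factors within the cohort. G2 selects none. The choice could therefore be made after the data are seen, and the same data could then be read as no difference or as a clear one.

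G1 adds to the problem. It justifies the sample by a hypothesis test for a gain in success, while G2 contains no matching test.

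**Working it through.** **Inputs.** From G1: reference failure 7.1%, a 20% increase in success, alpha 0.05, power 80%, 99 required, 10% dropout, 150 enrolled. From the background: 18%. Assumed: counts of 11 and 27 misplaced among 150, chosen near 7.1% and 18% for illustration only.

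**1. G1's own figure.** Success at baseline is 1 − 0.071 = 0.929. Adding 20 points gives 1.129; multiplying by 1.2 gives 1.115. Both exceed 1. The largest possible gain is 7.1 points, or 7.1/92.9 = 7.6% relative.

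The figure of 99 was then sought under nearby readings:
- One-sample proportion, 7.1% against 27.1% failure: n = [(z_α√(p0q0) + z_β√(p1q1))/δ]². Two-sided: [(1.960 × 0.257 + 0.842 × 0.444)/0.20]² ≈ 19.2, so 20. One-sided: 16.
- One-sample mean, n = [(z_α + z_β)SD/δ]² with δ = 0.20: SD √(0.071 × 0.929) = 0.257 gives 11 (one-sided) or 13 (two-sided); SD 0.5 gives 39 or 50.
- A 20% relative fall in failure, 7.1% to 5.68%: about 1,890 (one-sided) to 2,420 (two-sided).

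To reach 99 with δ = 0.20, two-sided, SD must be about 0.71. A single yes/no outcome cannot have an SD above 0.5. A paired difference can, but G1 states no such SD. Testing 7.1% against 18%, with the variance taken at 18%, gives 98, but G1 does not state that either.

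**2. What the odds ratio could be.**

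*Own control, before against after the re-do.* F2 repeats placement until ultrasound confirms it, so the reverse cell is close to empty by design. The paired ratio is b/c, with exact limits L/(1 − L) from the binomial interval on b/(b + c):
- 11 against 0: no finite estimate, lower limit 2.5, no upper limit.
- 11 against 1: 11 (1.6 to 473).
- 11 against 2: 5.5 (1.2 to 51).

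*Own control, provider's statement against the ultrasound verdict on the same injection.* Here b is called in but seen out, and c is called out but seen in. Both cells can fill, so a finite ratio is possible. It leaves out placements that both call out, which are blind failures too. It therefore measures recognition of misplacement, not the failure rate.

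*A fixed reference.* OR = odds(x/n)/odds(reference). The reference odds are 0.071/0.929 = 0.0764 and 0.18/0.82 = 0.2195; the observed odds are 11/139 = 0.0791 and 27/123 = 0.2195.

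| Misplaced | Against 7.1% | Against 18% |
|---|---|---|
| 11/150 | 1.04 (0.51 to 1.91) | 0.36 (0.18 to 0.67) |
| 27/150 | 2.87 (1.82 to 4.38) | 1.00 (0.63 to 1.53) |

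Limits come from the exact interval on x/n and treat the reference as a known constant.

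**3. The proportion itself (Clopper-Pearson).** 11/150 = 7.3% (3.7% to 12.7%); 27/150 = 18.0% (12.2% to 25.1%).

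Expected half-width of the 95% CI, averaged over the binomial distribution:

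| Evaluable | True rate 7.1% | True rate 18% |
|---|---|---|
| 99 | 5.5 points | 7.9 points |
| 135 (150 × 0.9) | 4.7 points | 6.8 points |
| 150 | 4.4 points | 6.4 points |

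**4. A one-sample test instead.** For illustration, an exact test against 7.1% with upper-tail alpha at most 0.025 has power at a true 18% of 92% with 99 patients, 96% with 135 and 98% with 150.

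**The case against.** The strongest reply is that a comparator can be found. Section I speaks of ultrasound being superior to the blind technique for recognising wrong placement, and F2 yields the data: the provider's statement and the ultrasound image of the same injection. That is a natural meaning of own control, and its odds ratio can be finite. This stands, so a reader who infers that any own-control odds ratio is degenerate goes too far; that holds only for before against after the re-do. But G2 does not name this comparison, and it answers a different question from objective 1.

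Second, the illustration is partly built in: counts set near 7.1% and 18% must give ratios near 1 against those values. The references are also not constants, and the documents give no denominators. If each came from an assumed sample of 50 to 150, Wald limits for 27/150 against 7.1% run from 0.90–9.13 to 1.36–6.08, and for 11/150 against 18% from 0.14–0.93 to 0.17–0.76. The exact limits shown are therefore too narrow for a comparison of two samples. The dependence on the comparator remains.

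Third, precision is not the only repair. A one-sample test against a named reference is feasible, and choosing between the two is partly preference.

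Fourth, this is a self-described pilot and G2 does report number and percentage, from which a reader could calculate the interval. That limits the harm. It does not make the planned interval the right one.

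**Conclusion.** The point holds and should be fixed. G2's only interval for the primary outcome is on a ratio whose second term is undefined, while the objective is a single rate. With 11/150, the choice between the two quoted references moves the estimate from 1.04 to 0.36; with 27/150, from 2.87 to 1.00. The 18% is moreover a heart-rate failure rate, not a location on ultrasound.

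Three stronger conclusions might be inferred and are not supported. G2 does not omit the failure rate; it omits the interval. An odds ratio is not impossible; several could be calculated, but none is specified. And 150 is not shown to be too few: 99 does not follow from G1's stated inputs, but 150 gives usable precision and would support a one-sample test.

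The sizes rest on hypothetical counts, on 7.1% and 18% as illustrative true rates, and on 10% dropout. One matter is for the sponsor: blind failure could mean any first placement outside the space, or only misplacement that the provider does not recognise. Objective 1 supports the first; the emphasis on unnoticed sham blocks in the background and Section I gives the second some weight.

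**What to change.** **G2.** Replace the odds-ratio sentence. Primary analysis: the proportion of patients whose first blind placement is outside the epidural space on ultrasound, with an exact (Clopper-Pearson) 95% CI. Separately, cross-tabulate the provider's first statement against the ultrasound verdict on that placement, and report the proportion misplaced but called correct, with an exact CI; this addresses the recognition claim in Section I. The sponsor should confirm which proportion is meant as primary. Drop the odds ratio, or name its comparator before data are seen and label it secondary.

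**G1, with N unchanged.** Withdraw the 20% gain and the 99. Restate the rationale in one of two ways:
- as precision: with 135 evaluable of 150 enrolled, the expected half-width of the 95% CI is 4.7 points at a true rate of 7.1% and 6.8 points at 18%; or
- as an exact one-sample test against a named reference that uses the ultrasound definition of failure.

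**Cost.** Two places are reworded, after one decision by the sponsor on the primary proportion. Procedures do not change, since F2 already generates both the statement and the verdict. The data sheet is not in the text reviewed, so confirm that it records both for the first placement. The 80% power claim for 99 patients is lost, and under the precision option there is no comparative p-value for the primary outcome.
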